2.8 Blinding

Due to the nature of the trial intervention, children and their parents will not be blinded to treatment allocation. A co-investigator who is blinded to group allocation will conduct outcome assessments. To ensure that outcome assessment is blinded, the principal investigator and co-investigator from each NICU must develop a local blinding procedure describing the workflow. This process will be approved by the central trial unit before study commencement. Data managers, statisticians and those writing the abstracts as well as drawing conclusions will also be blinded.

2.9 Participation criteria

All NICUs participating in the SafeBoosC-III trial will be invited to participate in the follow-up study. In the spring of 2021, NICUs will receive an official invitation to participate, along with this protocol, which has been approved by the Steering Committee. NICUs will be asked to state explicitly what data they will provide in the follow-up and as well as their expected follow-up percentage. NICUs will be encouraged to provide as much data as possible since this will strengthen the quality of the study.

The tasks for NICUs are as follows:

1. Obtain addendum ethical approval to conduct the follow-up study in their NICU, if necessary.

2. Obtain addendum contract and legal approval, if necessary
3. Delegate the review of health care records and outcome assessment to a co-investigator, who can be blinded to the group allocation in the SafeBoosC-III trial.
4. Develop local work flow and blinding procedure
5. Ensure that the contact information, ideally e-mail addresses of the parents, is maintained and that links to the web-based platform with the PARCA-R questionnaire and the health and development questionnaire are forwarded to the parents as necessary

Parents of all infants included in the SafeBoosC III trial, and alive at the time point where routine follow-up assessments are initiated, should be invited to participate in the follow-up study.

Since the first randomised infant in SafeBoosC III will reach two years of corrected age in September 2021, we expect that follow-up assessments will begin around this time point. The last follow-up assessment is expected to be completed before the end of 2024 since this is the time where we expect the last randomised infant to reach two years of corrected age plus six months of reserve.

2.10 Ethical considerations

2.10.1 Ethical review

The need for supplementary approval of the follow-up study by a Research Ethics Committee (REC) may differ among countries. In some countries, an REC approval may be an addition to the approval of the randomised clinical trial.

As the SafeBoosC-III follow-up study does not include exposures to any additional interventions, there is no safety risk for children. Thus, an interim analysis is not necessary.

2.10.2 Consent

When infants were randomised in the SafeBoosC-III trial, the parents were made aware of the possibility of a potential follow-up study and permission to contact families as foreseen in the information sheet the parents were given at inclusion. The study-related interventions consist of extracting data from health care records, and parental questionnaires. The need for explicit consent for using clinical data from health care records for the SafeBoosC-III follow-up study may differ

between countries. In some countries, turning up for examination or answering questionnaires will be considered sufficient, implicit consent.

2.10.3 Transfer of data

Permissions for data collection and transfer to the central trial unit in Copenhagen must be obtained according to local/national regulations. If necessary, the contract between the partners must be extended.

2.11 Resources

The cost of the central trial unit is covered by the sponsor, while the costs of the NICUs is covered locally or nationally.

2.12 Data management plan

All the participating children's data are protected in accordance with the Danish Act on the processing of personal data and the Danish Health Act. Data entry will be managed through a web-based clinical trial software, OpenClinica, provided by Copenhagen Trial Unit. The electronic case report form has already been used as the platform for data entries in the SafeBoosC-III trial, using end-to-end encryption. For this follow-up study, an additional data entry module will be added to the SafeBoosC-III OpenClinica setup. Data will be stored in accordance with guidelines issued by the Danish Data Protection Agency, where the follow-up study will also seek approval from. Data are pseudonymised, only NICU numbers and study numbers are used to identify children. Personal identifying information linking to study numbers will be kept in the trial master file at the local NICU.

Six months after the acceptance of the main publication presenting the primary outcome, the dataset will be transferred to the Danish data archive, after re-coding of variables (birth weight, gestational age, sex, NICU, study number) that may be used for reidentification. This data set can be made available for others as decided by the trial steering committee. Due to the residual risk of re-identification, the dataset will not be placed in public space.

3 Statistical analysis plan

Full details regarding statistical considerations and data analysis will be outlined in a separate report, which will be published before the analysis of the SafeBoosC-III trial data, expected late spring 2022.

Power estimations for the co-primary outcomes

The sample size of 1600 infants for the SafeBoosC-III trial is based on mortality and the prevalence of survivors with severe brain injury in the SafeBoosC II trial, i.e. a 22% relative risk reduction in the composite primary outcome from 34% to 26.5% (absolute risk reduction of 7.5%), at an alpha level of 5%, and a power of 90%. The latest Data Monitoring Report from March 2021 revealed a tentative mortality rate of 21% in the SafeBoosC-III trial, based on first 580 randomised infants. Assuming the mortality rate will stay constant, there will be 1264 infants alive at two years of corrected age, and thus, be available for follow-up assessment.

Death or moderate-or-severe neurodevelopmental disability power calculation

Based on answers from the questionnaire on systematic routine follow-up, as well as implementing parental questionnaires and informal assessments to classify neurodevelopment, we estimate the total sample size for the outcome death or moderate-or-severe NDD to 1600 children.

Based on results from two randomised controlled clinical trials (49,50) investigating neuroprotection in preterm infants, it is estimated that the proportion of children with the outcome death or moderate-or-severe NDD will be 50% in the control group. An indicative power calculation shows that if we want to test an absolute risk difference of eight percentage, between the experimental and control group, at an alfa of 2.5% and a sample size of 800 infants in each group, i.e. a total of 1600, we will reach a power of 80%.

Bayley III/IV mean cognitive score power calculation

Based on answers to a questionnaire on systematic routine follow-up from participating NICUs in the SafeBoosC-III consortium (see section 1.5 ‘recruitment and loss to follow up), it is expected that 65% of the NICUs will be able to provide data from a Bayley III/IV assessment around two years of corrected age for each child. Assuming that these NICUs enrol their proportion of the 1600 infants to the SafeBoosC-III trial, and a mortality rate of 21% (12), approximately 850 infants will be available for Bayley III/IV assessments at two years of age.

An indicative power estimation shows, that if we want to test a mean difference of five points on the Bayley cognitive score, with a standard deviation of 20 (Cohens d' 0.25) between the experimental and the control group, at a 2.5% alfa-level, with a sample size of 425 infants from each group in the follow-up study i.e. a total of 850, we will reach a power of 90%.

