Power calculation: Based on answers from the questionnaire on systematic routine follow-up, as well as implementing parental questionnaires and informal assessments to classify neurodevelopment, we estimate the total sample size for the outcome death or moderate-or-severe NDD to 1600 children. Based on results from two randomised controlled clinical trials investigating neuroprotection in extremely preterm infants, it is estimated that the proportion of children with the outcome of death or moderate-or-severe NDD will be 50% in the control group.

An indicative power calculation shows that if we want to test a risk difference of eight percent between the experimental and control group, at an alfa of 2.5% and a sample size of 800 infants in each group, i.e. a total of 1600, we will reach a power of 80%.

Continuous effect measure: mean Bayley III/IV cognitive score

The cognitive scores from the Bayley III/IV assessment will constitute a single continuous outcome measure.

Power calculation: Based on answers to an investigator questionnaire, we expect to have access to data from Bayley III/IV assessments of 850 children. An indicative power estimation shows that if we want to test a mean difference of five points on the Bayley cognitive score, with a standard deviation of 20 (Cohens d' 0.25) between the experimental and the control group, at an alfa of 2.5%, and a sample size of 425 infants from each group i.e. a total of 850, we will reach a power of 90%.

The exploratory outcomes will be daily medication the last two months (yes/no), any other chronic illness (defined as any problem which has been diagnosed by a doctor and which 1) is expected to last more than a few months, 2) causes problems in everyday life, or 3) is a risk of early death or disability), mean head circumference, mean height and mean body weight.

All components of the co-primary outcomes will be reported for the two groups separately as well as effect estimates with confidence intervals and will be taken into consideration when interpreting the main results

Time plan

The first randomised infant in SafeBoosC III will reach two years of corrected age in September 2021, while the last follow-up assessment is expected to be completed before the end of 2024, which is an estimate of when the last infant randomised will reach two years of corrected age plus six months of reserve.

Organisation and funding

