1.5 Recruitment and loss to follow-up

Loss to follow-up in studies with long-term outcomes is common and data are rarely missing completely at random. Studies have shown that children lost to follow-up often have a lower socioeconomic status and tend to have more neurodevelopmental impairment than children participating in follow-up programmes (41). Factors affecting loss to follow-up include maternal education, age, substance abuse, poverty level, and marital status, among others (42). As this is a pragmatic study, we do not expect that all eligible children will participate. However, we aim to ascertain follow-up data on as many children as possible by collecting data from all health care records from 12 months' corrected age onward as well as by parental questionnaires (see Methods section 2.6 'outcome assessment tools').

In the Summer of 2020, when recruitment was well-established, a questionnaire was sent out to all active NICUs asking if they were interested in participating in the follow-up study and how their local follow-up programmes were structured. Sixty-two NICUs completed the questionnaire and all expressed interest in taking part in the two-year follow-up study. All NICUs reported having a systematic follow-up programme of extremely preterm infants. Eighty percent reported a routine follow-up rate of 75% or more, and 65% routinely perform a Bayley III/IV assessment between 18 and 30 months' corrected age. Furthermore, several other standardised developmental assessments and screening methods were reported to be utilized from 18 to 30 months' corrected age, including Griffiths, Denver Developmental Screening Test II, Peabody II, Gessell, Ages and Stages Questionnaire, PARCA-R, Alberta Infant Motor Scales, etc. Almost all NICUs conduct a standardised neurodevelopmental assessment around two years' corrected age. Based on these investigator questionnaire responses, we have planned the SafeBoosC-III two-year follow-up study.

Since the summer of 2020, more NICUs have joined the SafeBoosC-III consortium, thus strengthening the chances of obtaining sufficient statistical power for a meaningful test of the intervention's effect on neurodevelopment.

2 Methods

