2.7 Data extraction

All data extraction from health care records and data entry into the e-CRF will be done by an assessor who is blinded to group allocation (see section '2.8 Blinding'). The co-primary outcome

Bayley III/IV mean cognitive score will be extracted from the records of the Bayley III/IV test. The co-primary outcome death or moderate-or-severe NDD will primarily be based on an assessment of available health care records, from when the child was between 18 and 30 months' corrected age. If more than one formal neurodevelopmental assessment has been conducted, the score of the latest should be used. If formal assessment of all four components is not available, the central trial unit will substitute the missing components with answers from parental questionnaires (PARCA-R and health and development questionnaire). The answers from the questionnaires will be reported directly by the parents to the central trial unit. If answers from parental questionnaires are not available, either the PI will be contacted by the central trial unit and requested to provide an informal assessment of the presence or absence of moderate-or-severe NDD. The assessment should be based on all available information from the child from at least 12 months' corrected age. For additional details on this approach, see appendix A.

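### The Bayley co-primary sample size of 850 does not follow from its stated inputs (about 822) and allows for no untested children, so 90% power at SD 20 needs about 97% of the 822 tested

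*Combined protocol and SAP*

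**What the plan says.** The power calculation for the continuous co-primary outcome in section 3 names three inputs: 1600 randomised infants, mortality of 21%, and 65% of NICUs that "will be able to provide data from a Bayley III/IV assessment around two years of corrected age for each child". From these it concludes that "approximately 850 infants will be available for Bayley III/IV assessments at two years of age". It then takes 425 per group, a difference of 5 points, SD 20 and alpha 2.5%, and reports 90% power. The Summary repeats the figure: "we expect to have access to data from Bayley III/IV assessments of 850 children".

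Other parts of the document bear on this number:

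- The start of section 3 says that "there will be 1264 infants alive at two years of corrected age, and thus, be available for follow-up assessment".
- Section 1.5, which the calculation cites as its source, reports of the responding NICUs: "Eighty percent reported a routine follow-up rate of 75% or more, and 65% routinely perform a Bayley III/IV assessment". It also says: "As this is a pragmatic study, we do not expect that all eligible children will participate".
- Section 2.7 says the "Bayley III/IV mean cognitive score will be extracted from the records of the Bayley III/IV test". Questionnaires and informal assessment can fill gaps in the disability outcome, but not in this one.
- Section 2.9 says "NICUs will be asked to state explicitly what data they will provide in the follow-up and as well as their expected follow-up percentage". The power calculation neither uses those returns nor says it will be updated from them.

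**The concern.** There are two separate problems. First, multiplying the three stated inputs does not give 850. Second, the calculation treats every survivor at a Bayley-using NICU as tested. The survey behind it shows only that those units use the test as routine, which says nothing about how many children complete it. A child without a Bayley record contributes nothing to this outcome, so each untested child is a direct loss of information.

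The Bayley score is one of two co-primary outcomes, and under section 3.1 either one can support a claim of superiority. Section 1.2.1 itself raises type II error as a possible explanation for the neutral phase II follow-up. If the 90% figure depends on near-complete testing, a reader will give a null Bayley result more weight than the design supports. Enrolment is fixed by the parent trial and is not affected.

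**Working it through.** **Inputs.** From section 3: 1600 infants, 21% mortality, 65% of NICUs, difference 5, SD 20, equal groups. Alpha is 0.025, from the Bonferroni rule in section 3.1. Sidedness is not stated; I take it as two-sided.

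**The plan's power figure.** With the two-mean normal approximation, power = Φ(5 / (20 × √(4/N)) − 2.2414). At N = 850 this is Φ(3.644 − 2.241) = 92.0%, consistent with the stated 90%. A one-sided 2.5% test would give 95.4%, so two-sided is the closer reading.

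**The plan's N.**
- 1600 × 0.79 = 1264, which matches section 3.
- 1264 × 0.65 = 821.6, about 822. This is 28 (3.3%) below 850.
- The Summary's rounded 1250 survivors give 1250 × 0.65 = 812.5.
- Reaching 850 would need 850/1264 = 67.2% of survivors, or mortality of 1 − 850/(1600 × 0.65) = 18.3%. The calculation states neither.

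**Children needed for 90% power.** n per group = 2 × (20 × (2.2414 + 1.2816)/5)² = 397.2, so 398 per group and 796 in total. 796/821.6 = 96.9%, and 822 − 796 = 26 children may go untested. Against the stated 850 the share is 796/850 = 93.6%.

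**Power by share tested, SD 20.** The difference detectable with 90% power is 3.523 × 20 × √(4/N).

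| Share of 822 tested | N | Power for 5 points | Difference detectable with 90% power |
|---|---|---|---|
| 100% | 822 | 91.0% | 4.9 |
| 95% | 781 | 89.5% | 5.0 |
| 85% | 698 | 85.6% | 5.3 |
| 75% | 616 | 80.5% | 5.7 |

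The last two rows borrow the only follow-up figures in the document: 115/135 (85%) in phase II (section 1.2.1), and the 75% threshold that 80% of NICUs reported meeting (section 1.5). Both describe general follow-up, not Bayley completion.

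**Dependence on the SD.** The largest SD that still gives 90% power is 5 × √(N/4)/3.523: 20.3 at 822, 19.8 at 781, 18.7 at 698 and 17.6 at 616. Section 1.2.1 gives phase II Bayley II SDs of 19.5 and 14.7. Their unweighted pooled value is √((19.5² + 14.7²)/2) = 17.3, which gives about 94% power at 698 and 91% at 616. SD 19.5 alone gives 87% and 83%. Bayley II is a different edition, so this is a range only.

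**The other co-primary outcome.** For 50% versus 42% with 800 per group at alpha 0.025 and a pooled-variance test, power is 83.4% against the stated 80%. No error is claimed there.

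**The case against.** The strongest reply is that nothing is shown to fail. The plan calls the number approximate and the power indicative, and at 822 power still exceeds 90%. The 65% is a share of NICUs; if those units enrol slightly more than their share of infants, 67.2% would give 850. The assumption of a score for each child is stated openly. No Bayley completion rate is given, so no actual shortfall is demonstrated, and at a pooled phase II SD of 17.3 the 90% would survive both lower scenarios. The full SAP is still to come, and a null result will in any case be read from the achieved N and its confidence interval.

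Much of this stands as a limit on the point. The 850-to-822 gap is small, the completion rates are scenarios, and the result depends on the SD. It does not remove the point. The section assumes that these NICUs enrol in proportion, which makes 65% the natural multiplier, and nothing in the documents supports a higher share. Stating an assumption does not reconcile it with the cited source, which expects incomplete participation. SD 20 is the plan's own value, and the phase II SDs do not settle the matter. Sections 3 and 3.1 promise a fuller plan, but not a revised power calculation.

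**Conclusion.** The concern holds. The stated inputs give about 822 children, not 850, and no factor for untested children is applied. The arithmetic slip alone costs about one percentage point of power (92.0% to 91.0%). The omitted completion factor matters more: at the plan's SD of 20, the 90% claim needs 96.9% of the 822 tested, and at 75% tested the chance of missing a true 5-point difference is 19.5%, about twice the stated 10%.

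This rests on a two-sided alpha of 2.5%, SD 20, equal groups and a simple two-mean formula that ignores the site random effect and the gestational-age term in section 3.1. Under a one-sided 2.5% reading, 674 children (82% of 822) would suffice. With an SD of 17.6 or less, 90% holds even at 75% tested. The consequence lies in how a null Bayley result is read, not in enrolment or conduct. It should be fixed.

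**What to change.** In section 3 and in the Summary, replace 850 with about 822 before non-completion, and show the product 1600 × 0.79 × 0.65. Then apply an explicit completion factor and restate the power. Take the factor from the NICUs' returns under section 2.9 once they are in, using what each unit says about Bayley data in particular as well as its overall follow-up percentage. Until then, show the four rows above (100%, 95%, 85%, 75%), labelled as scenarios, and state that they hold at SD 20 and would be higher with a smaller SD. Carry the same figures into the separate SAP.

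The cost is one figure changed in two places and a four-row table. No extra enrolment or change of conduct follows. The only downside is a less favourable stated power for the Bayley outcome.

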3.1 Primary analyses

The primary analysis of all outcomes will be based on the intention-to-treat population. Mixed-effect linear regression and mixed-effect logistic regression will be used to analyse the dichotomous and continuous co-primary outcomes, respectively. Data from all participating sites will be used in the primary analysis of both co-primary outcomes. In the regression models, 'site' will be included as a random effect, while 'gestational age below or above 26 weeks of postmenstrual age' and 'group allocation' will be included as fixed effects. To correct for multiple testing, the threshold for statistical significance will undergo Bonferroni adjustment, and thus a p-value of 0.025 for each primary outcome is chosen. Superiority of the intervention will only be claimed if at least one of the two co-primary outcomes is statistically significant. All other outcome results will be considered hypothesis-generating only. In addition, we will perform a range of pre-defined sensitivity analyses to inform the interpretation of the results of the primary analysis. A full statistical analysis plan will be developed and submitted for publication before the analysis of the SafeBoosC-III trial data.

[figure not shown]

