In total, 1600 infants will be randomised in the SafeBoosC-III trial. We expect approximately 1250 infants to survive and potentially be available for follow-up.

Inclusion criteria: Participation in the SafeBoosC-III trial and enrollment in a neonatal intensive care unit (NICU) taking part in the follow-up study, with parental consent according to local regulations.

Exclusion criteria: Parental objection to the use of their child's data in the follow-up study.

Participation criteria for NICUs: All NICUs participating in the SafeBoosC-III trial will be invited.

Assessments: We aim to collect follow-up data on as many children as possible by including data from routine neurodevelopmental follow-up programmes, utilizing all other health care records from the age of at least 12 months and by parental questionnaires including the PARCA-R.

Blinding: Due to the nature of the trial intervention, children and their parents will not be blinded to treatment allocation. A local co-investigator who is blinded to group allocation will conduct outcome assessments. To ensure that outcome assessment from health care records is blinded, the principal investigator and the co-investigator from each NICU will develop a local blinding procedure describing their individual workflow. Each local NICU blinding process will be approved by the central trial unit. Data managers, statisticians and those writing the abstracts as well as drawing conclusions will also be blinded.

Outcomes

There will be two co-primary outcomes:

Dichotomous effect measure: death or moderate-or-severe neurodevelopmental disability

A child will be classified with moderate-or-severe neurodevelopmental disability if any of the following conditions are present: cerebral palsy with a Gross Motor Function Classification Score ≥ 2 ; a cognitive function score below -2 standard deviations from the norm (or Bayley-III/IV < 85); hearing impairment; or vision impairment. Available data from at least 12 months' corrected age from health care records, including standardised neurodevelopmental assessments, as well as parental questionnaires completed between 18-30 months' corrected age will be used to assess mortality and neurodevelopment.

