2.4.2 Exploratory outcomes

The exploratory outcomes are as follows:

- Daily medication the last two months (yes/no)
- Any other chronic illness (defined as any problem which has been diagnosed by a doctor and which 1) is expected to last more than a few months, 2) causes problems in everyday life, or 3) is a risk of early death or disability)
- Mean head circumference
- Mean height
- Mean body weight, with one decimal

All components of the co-primary outcomes will be reported for the two groups separately as well as effect estimates with confidence intervals and will be taken into consideration when interpreting the main results

All outcomes will be assessed from health care records by a blinded assessor at a minimum of 12 months of corrected age.

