For the purpose of the co-primary outcome Bayley III/IV mean cognitive score, the unadjusted mean scores from the experimental and control group will be compared. If the Bayley III/IV cognitive score is used to evaluate cognitive function in co-primary outcome death or moderate-or-severe NDD, the cognitive function cut-off will be <85 , as done in previous trials and recommended by experts (35).

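### Section 3.1 swaps the two primary models: linear regression goes to the yes/no composite and logistic regression to the Bayley score

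*Combined protocol and SAP*

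**What the plan says.** Section 3.1 (Primary analyses) sets out the confirmatory analysis: intention to treat, site as a random effect, gestational-age group and allocation as fixed effects, and a threshold of 0.025 for each co-primary outcome. The models are named in one sentence: "Mixed-effect linear regression and mixed-effect logistic regression will be used to analyse the dichotomous and continuous co-primary outcomes, respectively".

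Which outcome is which is settled elsewhere:

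- Summary, Outcomes, on the composite: "Dichotomous effect measure: death or moderate-or-severe neurodevelopmental disability".
- Summary, Outcomes, on the Bayley score: "The cognitive scores from the Bayley III/IV assessment will constitute a single continuous outcome measure".
- Section 2.6.1, on the Bayley co-primary: "the unadjusted mean scores from the experimental and control group will be compared".
- Section 3, power calculation for the composite: "test an absolute risk difference of eight percentage, between the experimental and control group".
- Section 3, power calculation for the Bayley score: "a mean difference of five points on the Bayley cognitive score, with a standard deviation of 20".

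Section 2.4.2 promises, for the components of the co-primary outcomes, "effect estimates with confidence intervals and will be taken into consideration when interpreting the main results", but names no effect measure. Section 3 opens by deferring detail: "Full details regarding statistical considerations and data analysis will be outlined in a separate report". That report is not among the documents.

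**The concern.** The sentence lists the models as linear then logistic and the outcomes as dichotomous then continuous, and 'respectively' ties them together in that order. Each outcome therefore receives the model that suits the other. No other section names a regression model for either co-primary outcome, so nothing in the document corrects it.

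The two halves fail differently. Logistic regression on raw Bayley scores is not possible, so anyone following the text has to depart from it. A linear mixed model on a 0/1 composite does run. It returns a risk difference, which is the scale on which the composite was powered, so a reader could take that half as a deliberate choice. What is at stake is the effect measure reported for a confirmatory outcome. There is also a risk that a correct logistic analysis later looks like a departure from the protocol.

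**Working it through.** **Step 1. Match the order in 3.1 to the outcome labels.**

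| Outcome | Type in the Summary | Basis of its power calculation (section 3) | Model in 3.1, read literally | Model that fits the type |
|---|---|---|---|---|
| Death or moderate-or-severe NDD | Dichotomous | Risk difference, 8 points from 50% | Linear | Logistic |
| Bayley III/IV cognitive score | Continuous | Mean difference 5, SD 20 | Logistic | Linear |

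Both rows are reversed.

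**Step 2. Confirm from the power figures how each outcome was treated.** Two-sided alpha 0.025 is assumed, since 3.1 does not state sidedness; z = 2.2414.

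- Composite, as two proportions, 0.50 versus 0.42, 800 per group. SE under the null = sqrt(2 × 0.46 × 0.54 / 800) = 0.02492. SE under the alternative = sqrt((0.25 + 0.2436) / 800) = 0.02484. Power = Φ((0.08 − 2.2414 × 0.02492) / 0.02484) = Φ(0.972) = 83.4%. The plan states 80%.
- Bayley, as two means, 425 per group. SE = 20 × sqrt(2 / 425) = 1.372. Power = Φ(5 / 1.372 − 2.2414) = Φ(1.403) = 92.0%. The plan states 90%.

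The stated figures are somewhat lower than these, which is the cautious direction and not part of this point. What matters is that the planners treated the composite as binary and the Bayley score as continuous, the opposite of the literal pairing.

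**Step 3. Can the literal model be fitted to the Bayley score?** Binary logistic regression needs a 0/1 outcome. The cut-off of 85 in sections 2.4.1 and 2.6.1 serves the cognitive component of the composite, and its use in Appendix C belongs to ancillary studies. For the Bayley co-primary the plan compares means and foresees neither a cut-off nor a rescaling. A trial fit to 850 simulated raw scores (mean 90, an assumption; SD 20) was refused because the values lie outside 0 to 1.

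**Step 4. What would the literal model report for the composite?** Crude calculation at the planning values, ignoring site and gestational age:

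- Linear (risk difference): 0.42 − 0.50 = −0.080; SE = 0.02484; z = −3.22; p = 0.0013. 97.5% CI: −0.080 ± 2.2414 × 0.02484 = −0.136 to −0.024.
- Logistic (odds ratio): (0.42/0.58) / (0.50/0.50) = 0.724; ln = −0.3228. SE = sqrt(1/(800 × 0.25) + 1/(800 × 0.2436)) = sqrt(1/200 + 1/194.88) = 0.1007; z = −3.21; p = 0.0013. 97.5% CI: exp(−0.3228 ± 2.2414 × 0.1007) = 0.58 to 0.91.

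A simulated data set with 400/800 versus 336/800 events, spread over 62 sites (the number answering the questionnaire in section 1.5) with a gestational-age stratum, agreed. A linear mixed model on the 0/1 outcome gave −0.080 (SE 0.025), and a logistic regression gave 0.724.

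The evidence against the null is the same under either model; the reported quantity is not.

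**The case against.** The strongest reply is that this is a slip that misleads nobody. The outcome types are labelled plainly, the power calculations agree with the labels, and the Bayley half cannot be run, so a statistician who notices that will see that the whole pair is reversed. The composite test barely changes. Section 3 defers the detail to a separate plan, and section 3.2 has two statisticians analysing the data independently. Most of this stands: the intended order can be inferred, and no harm to the actual analysis has been shown. It does not make the sentence right. The sentence is the only statement of the two primary models, and a document that is not supplied cannot be relied on to correct it. Independent analysts also need a single unambiguous starting text.

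A second reply is that a linear model for the composite might have been wanted for its risk difference. The plan does not say so, and the same sentence would then still be wrong for the Bayley score.

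A third is that the odds ratio of 0.72 is crude, whereas the planned model conditions on site and gestational age. That is correct. Holding the margins at 50% and 42%, and assuming gestational-age odds ratios of 1 to 4 and a site SD of 0 to 0.8 on the logit scale (neither is in the documents), the conditional odds ratio is about 0.67 to 0.72. The shift is small and does not affect the point.

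**Conclusion.** The concern holds. As written, the rule for both confirmatory tests is reversed, and for the Bayley score it cannot be carried out. For the composite it would replace an odds ratio of about 0.72 with a risk difference of −8.0 percentage points at the planning values, with practically the same p-value. No sample size, alpha or power figure changes, and this is not a design flaw. The numbers rest on the plan's 50% and eight-point assumptions, a two-sided 0.025 level and no adjustment for site or gestational age. The reversal itself rests on the wording alone. Whether the separate analysis plan repeats it cannot be checked from the documents. It should be fixed before analysis.

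**What to change.** In section 3.1, state that mixed-effect logistic regression will be used for death or moderate-or-severe NDD and mixed-effect linear regression for the Bayley III/IV cognitive score. Naming the outcomes removes the dependence on word order. Leave the site, gestational-age and allocation terms as they are. Check that the separate full analysis plan uses the same pairing. The cost is one sentence and one cross-check, with no effect on data collection, participants or sample size.
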